## 6.2 Adequacy of Protection Against Risks

**6.2.a Recruitment and Informed Consent:** Potential subjects and their parents or guardians will first hear about the study from their pediatric otolaryngologists and associated office staff, at the time that the surgery is scheduled. A parent or guardian willing to hear more about the study will sign a brief consent, and on the same one-page form provide (in conjunction with the otolaryngologist) simple information about contact numbers, date of surgery, reason for surgery, symptoms of SDB, and likelihood of SDB. The form will be faxed to the investigators. Alternatively, parents of potentially eligible subjects may learn about the study from the study brochure provided to patients or the ClinicalTrials.gov posting. They may then request contact by a member of the study team. An investigator will call the parents to explain that:

- We are conducting a study on sleep disorders, behavior, and thinking in children who have AT for SDB;
- We believe a good number of children with SDB may be affected in these areas;
- Participation in the research will require either 2 or 3 separate overnight stays in the Sleep Laboratory;
- Some compensation to both parent and child will be provided for their time and effort;
- Some children (2/3) will be randomly assigned to use PAP at home nightly for 6 months, starting 4 months after AT; other children (1/3) will use no PAP during the same period;
- All data collected will be kept confidential;
- All participants are free to withdraw from the study at any time;
- Summary test results will be provided upon request within several months after final testing, when scored neuropsychology and sleep results from initial and follow-up sessions are ready;
- If preliminary review of test results suggests that something may need urgent medical attention, these findings will be communicated promptly to the family and treating surgeon.

During this initial phone call, data also will be gathered to ensure that the subject meets inclusion and exclusion criteria. Potential participants and their families will be invited to the Sleep Disorders Center to further review the above points, hear about the research protocol in more depth, tour the sleep rooms, see the equipment used during sleep studies, and see sample PAP equipment. At this time, a study team member will obtain signed permission / consent from a parent or guardian and assent from the child. Children older than 8 years or able to understand the nature of the research will be asked to sign assent; other children will be asked for verbal assent. One copy of the documents will be placed in the subject's medical record, one given to the parent, and one kept on file by [name].

**6.2.b Protection Against Risk:** Fatigue and anxiety during cognitive testing will be minimized by a neuropsychology technician who has extensive experience with children and will give breaks from testing as needed. If results of behavioral or cognitive assessments engender parental concern, the child and parents will be invited back to a meeting with a child psychologist co-investigator, who will discuss the findings in an appropriate manner and review options for further evaluation or treatment outside the research protocol. Prior to study enrollment, tours of the sleep laboratory will give subjects and families a preview of that environment and equipment used there, reduce any possible fears or anxieties, and give them a good understanding of study requirements in relation to family, school, and job commitments. Technicians experienced with children and anxieties of this age group will conduct sleep studies. Children will be offered a topical anesthetic prior to insertion of the esophageal pressure catheter. However, children who do not tolerate placement of the esophageal catheter (anticipated based on this group's past work to constitute a minority of these volunteer subjects) or other equipment will not be required to use them. Parents will stay with children during overnight testing to reduce separation anxiety. Spacious pediatric sleep rooms are designed to include a separate bed for the parent. We will instruct subjects who obtain poor sleep in the laboratory to avoid operating dangerous toys, bicycles, and machinery until adequate sleep is recovered. We will also ask parents to supervise such children at home until restorative sleep is obtained. During sleep studies, a physician investigator will always be on call for any unexpected emergencies. Studies will be performed at the Sleep Disorders Center in the 10-bed Michael S. Aldrich Sleep Disorders Laboratory, where a 24-hour technical staff including pediatric and research technologist pods is well prepared to meet the needs of children and families who participate in research. If a cutaneous reaction to electrode placement occurs, technicians will remove the electrode and reapply it at another site with a different type of adhesive. Mild skin irritation will be treated with topical creams as needed. Moderate reactions at multiple sites, or any severe reaction, will warrant study termination. Finally, every effort will be made to ensure, as in the investigators' past NIH-funded pediatric sleep protocols, that this research experience is fun, positive, and rewarding for each subject and family.

Problems with PAP use will be preempted in part by thorough education of parents, and children, about the purpose, potential benefits, and importance of nightly adherence. Participating families will be well educated about potential problems, and what to do about them, even before starting PAP. The PI has some of the earliest published experience with strategies to optimize CPAP adherence, and the investigators are thoroughly familiar with application of this therapy to children. Best efforts will be made first in the sleep lab, just prior to the CPAP titration study, and again at the visit to the durable medical equipment company, to make sure each child is optimally fitted for a CPAP interface (generally a nasal mask, though sometimes a face mask or nasal pillows). This will minimize risk for discomfort or irritation.

After PAP is initiated, contact initially with investigators will occur weekly (at least by phone) and will provide multiple opportunities to detect poor fit before this could lead to serious irritation, wound, or infection. Mask discomfort will be addressed as soon as it is apparent by re-adjustment of headgear straps, or trials of different mask models. Nasal congestion or mouth dryness, depending on the apparent cause, will be ameliorated by reducing any mouth leak (e.g., by using a chinstrap); use of a full face mask; nasal saline irrigation; or improved use of heated humidification. Use of PAP on every night will be encouraged: parents and children will be educated about its importance, what can happen if PAP is not used, and also the fact that an occasional night off PAP could have some consequence – but not enough to make an occasional exception (e.g., for a “sleep over” at a friend’s house) impossible. The concern that long-term use of a PAP mask could diminish growth of the mid-face will be broached, but presented as most unlikely to occur within a 6-month protocol.

Some children in this protocol will use PAP without having enough underlying, residual SDB to benefit from the intervention. During the treatment trial, neither investigators nor families will know who these children are. Although symptoms may be readily apparent, sleep study results will not be available until after study participation is complete, for several reasons. One is that sleep studies are to be scored in batches -- with several subjects’ pre-PAP and post-PAP studies all in the same de-identified batch -- to avoid any influence of scoring drift over time. A second reason is that at present, knowledge about how post-AT care should be guided by sleep study results remains quite limited. The research now proposed, in fact, aims in large part to address this void.

Fortunately, subjects without residual SDB after AT, as compared to subjects with SDB, have no known additional risks to use of PAP. When the PAP titration studies are performed, children without SDB will have normal breathing, technologists will have no reason to test more than the lowest CPAP settings, and the reviewing physician (co-investigator [name]) can be expected to assign the lowest settings for use at home. In other studies of adults, even CPAP at fixed pressure settings for all research subjects, whether healthy or ill, has been safe whether SDB is present or absent.

Families whose children have been randomized to the control group will be contacted by the program manager during the 6-month trial at intervals designed to replicate the frequency of investigator contacts in the CPAP group. Discussion will focus on recuperation after AT, general health, and also any suggestion of serious adverse effects that would warrant discontinuation of study participation and referral for clinical evaluation. These end-points would include recommendation by a child’s pediatrician or otolaryngologist to pursue this option; development of a new, serious cardiopulmonary condition that makes prompt assessment and treatment for any residual SDB imperative; or emergence of serious academic or developmental concerns in the setting of obvious, persistent symptoms of SDB. Each questionable case will be brought by the program manager to the PI and, depending on the nature of the event as outlined in the Data and Safety Management Plan, the DSMB(section 6.5 below) for a decision.

All information collected in the course of this protocol will be treated confidentially. Written authorization will be obtained from a parent or guardian prior to release of any study results, except in the rare case of emergent findings that require immediate attention of a child’s clinician. Applicable IRB, privacy office, and contract office approvals will be obtained prior to transfer of data outside the research team. Printed data will be stored in locked cabinets within a locked private office of the program manager. Data will be linkable to subject names only by a key kept separately from the data files. Computer data will be password-protected, accessible only by study personnel, and backed-up to prevent accidental loss. Published reports will not include names or make individual participants readily identifiable in other ways. These precautions are highly likely to maintain confidentiality effectively.

Any unforeseen urgent medical problems that arise during testing will be handled or triaged by the physician investigator on call and the technologists at the Aldrich Sleep Laboratory. This fully accredited facility studies about 5 children every night of the week for clinical or research purposes. Standard protocols are known by the technologists and readily available for emergencies such as fire, threatening arrhythmia, or seizure. Data and safety monitoring for this non-randomized clinical trial will proceed as outlined below.

### **6.3 Potential Benefits of the Proposed Research to Human Subjects and Others**

Each subject has a significant chance of substantive benefit, at comparatively low risk and expense. Each child will benefit by 1) free testing for residual, post-AT SDB; 2) family knowledge, if desired, of any residual SDB after the clinical trial is completed, to facilitate decisions about ongoing care thereafter; 3) identification of potentially treatable behavioral or cognitive problems that may not have been suspected or diagnosed in the past; 4) participation in research that past subjects and families have often found to be an enjoyable, educational, and rewarding experience; 5) development of positive attitudes toward clinical research and ability to serve as community liaisons who can raise awareness of SDB among other families and children at risk. In addition, families whose child has been randomized to the CPAP group may benefit from the free, gold-standard treatment for any possible residual SDB, with careful expert attention to PAP adherence for the duration of the trial. After families have completed the protocol, those from CPAP and control groups will be assisted with referrals for any sleep, behavioral, or mental health care that they would like to pursue. Children whose families and pediatricians would like them to remain on PAP will be able to keep the PAP equipment at no cost, which could be an important opportunity in some instances. The CPAP machines that will not continue to be used by CPAP group subjects will be returned to the investigators. These units will be made available to any control families who, with assistance from their child's physician, wish to use CPAP for clinical purposes after completion of the research protocol.

Potential benefits to other children of the data to be obtained in this study are significant. The long-term risks to sleep, health, cognition, and behavior of unrecognized and incompletely treated SDB after AT could be substantial. Diagnosis and treatment of residual SDB after AT – now believed to occur in half or more of operated children – could have significant impact on social, intellectual, monetary, and health-related spheres not only during childhood but into adulthood as well. Risks to the subject from this protocol are not more than “minor over minimal,” as described above. Therefore, the risk:benefit ratio for children who participate in this study and parents who assist them is excellent.

#### **6.4 Importance of the Knowledge to be Gained**

For society, the potential benefits are sizable. Sleep-disordered breathing has high prevalence among children (at least 2-3%) and is most commonly treated by AT. However, current data, perhaps in part because of increased childhood obesity, suggest that many children still have some residual SDB after the procedure is performed. This research will begin to clarify which methods best identify appropriate candidates for additional SDB treatment after AT, and what benefits can be expected from PAP in this setting. This research will provide some of the first data directly relevant to common clinical decisions – who to evaluate and who to treat further after AT – that at present must be made based largely on published pre-operative data that may not pertain. The potential impact of knowledge from this study will therefore be substantial, both in terms of improved health outcomes and reduced societal and healthcare costs for children with incompletely treated SDB. Risks of this research arise from testing procedures (neurobehavioral and sleep) that are commonly performed in children and generally rated as “minor over minimal risk” at most. Risks also arise from treatment with PAP, but this is not a systemic medication, remains non-invasive, and has overall an extremely favorable side-effect profile and safety record in children as in adults. Finally, risks may arise from randomization of some children to receive no PAP. However, in standard care the vast majority of children who have AT are offered no follow-up testing or treatment. In this protocol, all children will receive follow-up testing, and treatment will still be available outside the research protocol to any subject whose family decides to seek treatment as part of their standard clinical care. Therefore, risks for this study seem highly reasonable in relation to knowledge to be gained. No test article is to be used in this research.

#### **6.5 Data and Safety Monitoring Plan**

The goal of the data and safety monitoring plan (DSMP) will be to protect patient safety and ensure the integrity and validity of the data. We will achieve this with a protocol designed to monitor and report adverse events specifically related to the protocol evaluations and PAP treatment, monitor study progress, assess appropriateness of continuing or stopping the trial, ensure protocol compliance and data accuracy, and prevent biased interpretation of data or conflict of interest. We will register this trial in a clinical trial registry that meets

NIH approval. We will elaborate and modify this DSMP as necessary in working with the NIH to formulate acceptable approaches.

The original protocol was submitted to NIH and approved for funding with a medical monitor to oversee participant safety and data integrity. But, more recent discussions with the NIH program officer have led to the suggestion that this project may be better served by a data and safety monitoring board. Plans for a DSMB have not been elaborated in detail:

Data and safety monitoring for this randomized, controlled, single-site clinical trial comparing CPAP treatment to no CPAP treatment after adenotonsillectomy will be accomplished in part by a Data and Safety Monitoring Board (DSMB). The board will be composed of individuals with expertise relevant to this study, its participants, or the evaluations and interventions that are planned. The DSMB board members will be external to the investigators, external to the University of Michigan, and otherwise uninvolved in this research. The DSMB will be assembled and guided with assistance from the relevant Program Officer at the NIH. The DSMB will convene, at least annually, and generally by phone, to review and make recommendations regarding recruitment and retention, adverse events, any treatment safety concerns, and data quality or integrity. The Principal Investigator will review, grade, and report any adverse events, ORIOs, or unanticipated problems, with the assistance of the Program Manager, to the IRBMED, the DSMB, and the NIH program officer as required by the approved study-specific DSMP.

#### Adverse Events

The Principal Investigator will review and assess adverse events for nature, seriousness, severity, frequency, expectedness, and relatedness to the study interventions. Information on adverse events or other significant reportable occurrences on this protocol will be reported to the Data Safety Monitoring Board. The DSMB will be responsible for (1) periodic review and evaluation of participant safety, recruitment and retention, and study conduct, and for (2) recommendations for continuation, modification, or termination of this clinical trial. The DSMB will be notified of project-related, medical or psychological conditions, or adverse events that may require intervention. Protections against risks in the proposed research will include those detailed above (section 6.2.b). No new intervention, device, or drug is to be studied in this protocol, and risks are likely to be considered by the IRB as "minor over minimal," as in the past for other pediatric sleep research studies at the University of Michigan. The PAP equipment used in the treatment arm of this clinical trial is commercially available (by prescription) and commonly used for adults and children with SDB, though PAP is not specifically FDA-approved for use in children.

Adverse consequences related to sleep studies, cognitive testing, PAP treatment, or lack of PAP will be communicated by the Principal Investigator to the IRB and the DSMB, either individually or in aggregate reports, depending on the nature, frequency, severity, and seriousness of the event. The investigators will follow an approved study-specific IRB reporting plan for expected and unexpected adverse events, serious adverse events, and unanticipated problems. The PI, IRB, and the DSMB will be responsible for monitoring the safety of the study. The PI will characterize the nature and grade of the adverse event. Non-serious expected adverse events that may be reasonably anticipated to arise as a result of study procedures will be described in the consent form, recorded in practice, and reported to the IRB annually as part of the progress report. SAEs and UaPs related to the study will be reported within 7 days to the IRB, DSMB, and NHLBI program officer per the study-specific reporting plan (see the Data and Safety Management Plan). The PI or designee will notify the DSMB chair and NHLBI program officer about the occurrence of a SAE related to the study or any death regardless of attribution within 24-48 hours of the PI being notified of the occurrence. Non-serious, expected adverse events that occur with greater than anticipated frequency or severity will be reported to the IRB; consent forms will be modified as necessary; and subjects already enrolled will be advised accordingly. Unexpected, nonserious adverse events that are moderate to severe and related to the protocol will be reported to the IRB and DSMB within 14 days and to the NHLBI program officer within 30 day if the events are unanticipated problems. An expected but serious adverse event that is related to study interventions will trigger notification of the IRB, DSMB, and NIH program officer within 7 days of the event, or within 7 days of the date that the study team is notified of the event. Nonserious unanticipated problems or device effects will be reported to the IRB, DSMB and program officer within 14 days of study team awareness of the safety issue. Intercurrent events and adverse events that are nonserious and expected or not related to

the study interventions (for example, common childhood illnesses, peri- or post-operative events or sequelae) will not be reported with the exception of a subject death which will be reported in expedited manner regardless of attribution. Participating families will receive written directions and encouragement to contact an appropriate physician or nurse at any time, 24 hours per day, 7 days per week, about any medical concern or adverse event related to the research study. In addition, frequent phone and face-to-face contacts, as described in section C6 of the research strategy, will be maintained with each family during the clinical trial.

An adverse event log will be maintained by the Program Manager. The Program Manager will meet weekly with the PI to review study progress, any protocol deviations, and resolution of adverse events. The project and consent forms will be reviewed at least once each year by the IRB. The investigators will prepare a full report annually for the DSMB to summarize adverse events, responses of the investigators, and any changes to the protocol or consent and regulatory documentation.

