## C. APPROACH

**C1. Overview.** *We propose a single-center, randomized and controlled but not blinded clinical trial to assess what variables predict further response to CPAP after AT (Figure 1). Potential inclusion of any child, regardless of post-operative polysomnographic results at 4 months, will allow the full spectrum of polysomnographic results to be tested as predictors of neurobehavioral response to CPAP. Standard cut-offs used to define clinically significant SDB remain untested in the post-AT setting, but will be applied first to test hypotheses 1a, 1b, and 2a. Other cut-offs and continuous measures that have been proposed by our group and others also will be tested in key exploratory analyses that could prove highly informative. The protocol will allow for example assessment of the possibility that clinical symptoms as detected on a questionnaire, but too insensitive to register on polysomnography, still deserve treatment. Every child who participates in this protocol will stand a chance to benefit. Two-thirds will receive CPAP; no standard care will be denied; and at the end of the study, summaries of sleep and neurobehavioral findings will be made available to all families, along with guidance on how to obtain follow-up clinical care for any remaining concerns.*

**C2. Subjects.** Recruitment will be directed by co-investigator [name], a University of Michigan pediatric otolaryngologist, with the assistance of 4 additional otolaryngologists in the Division of Pediatric

Otolaryngology, and 4 at St. Joseph Mercy Hospital in Ann Arbor. Both groups of surgeons have energetically supported recruitment for the PI's sleep research on children undergoing AT for the past 10 years. Surgeons or clinic office personnel will ask each parent or guardian of a child scheduled to undergo full AT for suspected SDB whether he or she would be willing to hear about the research. If so, a brief signed consent will be faxed to the investigators, who will initiate discussion by phone and then invite the family to the sleep laboratory to

[figure not shown]

Figure 1

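### Section 6.5 contradicts itself on which adverse events reach the DSMB, and nothing calls for adverse events by randomised arm

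*Combined protocol and SAP*

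**What the plan says.** Section C1 describes a "randomized and controlled but not blinded clinical trial". Under section 6.5, Adverse Events, "The Principal Investigator will review and assess adverse events for nature, seriousness, severity, frequency, expectedness, and relatedness to the study interventions". No blinded or independent adjudication is described.

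The exclusion is a single sentence near the end of the reporting rules. It opens with "Intercurrent events and adverse events that are nonserious and expected or not related to" and continues with "the study interventions (for example, common childhood illnesses, peri- or post-operative events or sequelae) will not be reported". Its one exception is a death, which is expedited whatever its cause.

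Other parts of section 6.5 point towards fuller reporting:

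- The opening of the section has the DSMB meet at least once a year, with adverse events among the topics it reviews.
- The first paragraph of Adverse Events says that adverse event information goes to the DSMB.
- Adverse consequences of sleep studies, cognitive testing, PAP or the lack of PAP go to the IRB and DSMB, singly or in aggregate.
- "Non-serious expected adverse events that may be reasonably anticipated to arise as a result of study procedures" are to be recorded and reported to the IRB each year.
- The program manager keeps an adverse event log, and "The investigators will prepare a full report annually for the DSMB to summarize adverse events". No relatedness filter and no layout by arm is stated.

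**The concern.** The reporting rules depend on one person's judgement of each case, and that person knows the allocation. Section 6.1.c lists nasal congestion, mouth dryness, facial irritation and possible infection at an irritated site as risks of PAP. Congestion is also an everyday finding in children aged 5 to 12. A child with congestion falls under the PAP-related route if the investigator blames the mask, and under the exclusion if the investigator blames a cold. Such a call is hard to make child by child. The randomised control arm lets the question be answered in aggregate, by comparing how often the event occurs in each arm.

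Section 6.5 asks the DSMB to recommend whether the trial continues, changes or stops, and anticipates no interim analysis. The annual report is therefore the board's main cumulative view of safety. If the exclusion is applied as written, attribution made with knowledge of the arm decides what enters that view. The stakes are not trivial: section 6.2.b accepts that some children will use PAP without enough residual disease to benefit from it.

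**Working it through.** The plan states no adverse event rate and no safety power, so there is no figure to reproduce. The check is mainly a comparison of the rules.

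**Step 1: where each class of event goes under section 6.5.**

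| Event class | Route stated | Conflict or gap |
|---|---|---|
| Any death | Expedited, whatever the cause | None |
| Serious, judged related | DSMB chair within 24-48 hours; IRB, DSMB and program officer within 7 days | None |
| Serious, non-fatal, judged unrelated | No expedited route | Annual summary only, or nothing (step 2) |
| Non-serious, unexpected, related, moderate to severe | IRB and DSMB within 14 days | None |
| Non-serious, expected, from study procedures | IRB yearly; IRB again if more frequent or severe than foreseen | The exclusion sentence says such events are not reported; the DSMB is not named in these two rules |
| Non-serious, judged unrelated | Excluded | The annual DSMB summary carries no such filter |

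**Step 2: the two readings of the exclusion.** The words in "Intercurrent events and adverse events that are nonserious and expected or not related to" can be grouped in two ways.

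- Reading A: non-serious, and either expected or unrelated. Serious events lie outside the sentence. A non-fatal serious event judged unrelated still meets no expedited rule, because each of those is limited to related events or deaths. Its only evident route is the annual summary.
- Reading B: either non-serious and expected, or unrelated. The same serious event is then excluded altogether.

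The examples, such as ordinary childhood illness, suit reading A. The exception suits reading B: the rule is "will not be reported with the exception of a subject death which will be reported in expedited manner regardless of attribution", and a death would hardly need exempting from a rule confined to non-serious events. The wording does not settle it.

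**Step 3: arm.** Nothing in section 6.5 (including Data Monitoring and DSMB Reports), C3 or 6.2.b asks for adverse events by randomised arm. The Data Monitoring text promises summaries of enrolment, withdrawals and completions, also without a stated split.

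**Step 4: what a table by arm could show.** Inputs: 80 CPAP and 40 control children (section C9), two-sided 5% level. The event rates are assumed, since the documents give none. With control rate p1 (n1 = 40), CPAP rate p2 (n2 = 80) and pooled rate p̄ = (n1·p1 + n2·p2)/(n1 + n2):

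- se0 = √[p̄(1 − p̄)(1/n1 + 1/n2)]
- se1 = √[p1(1 − p1)/n1 + p2(1 − p2)/n2]
- power = Φ[(|p2 − p1| − 1.96·se0)/se1]

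For 20% v 40%: p̄ = (8 + 32)/120 = 0.333; se0 = √(0.2222 × 0.0375) = 0.0913; se1 = √(0.16/40 + 0.24/80) = 0.0837; power = Φ[(0.20 − 0.1789)/0.0837] = Φ(0.25) = 0.60.

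| Control v CPAP (assumed) | Power |
|---|---|
| 10% v 20% | 0.26 |
| 20% v 40% | 0.60 |
| 30% v 60% | 0.89 |

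For serious events at an assumed 1% to 5% in both arms, the expected counts are 0.8 to 4 with CPAP (80 × 0.01 to 80 × 0.05) and 0.4 to 2 in controls (40 × 0.01 to 40 × 0.05). At those counts, leaving out one event matters.

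**The case against.** The strongest reply is that the exclusion closes a run of rules about single events with deadlines. Read there, it may mean only that these events get no individual or expedited report, which would agree with the annual summary. That is plausible, and the proposed fix adopts it. But the sentence does not say so, and it still sits badly with the yearly IRB report of non-serious expected events.

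A reader might infer that the DSMB is barred from seeing these events. The documents do not support that: the board is to review adverse events, is to receive information and an annual summary on them, and under sections C3 and 6.2.b may be sent questionable control-arm cases. Nor do they establish that serious events judged unrelated are withheld, because that depends on reading B. A reader might also infer that the rule on events more frequent than foreseen is disabled. That does not follow: the investigator is to "assess adverse events for nature, seriousness, severity, frequency, expectedness, and relatedness to the study interventions", and reviews progress and adverse events weekly with the program manager, who keeps the log, so the rule does not depend on earlier reporting.

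Three further points stand as limits. The Data and Safety Management Plan and the study-specific IRB reporting plan are cited but not available here, and either may settle the matter. Counts by arm are not free of bias, since families know the allocation and the CPAP arm has additional mask and adherence contacts, although control contacts are meant to match in frequency. And power is low for all but large excesses, with less still at annual looks during accrual. A board nonetheless needs the counts, whether or not they reach significance.

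**Conclusion.** The point holds as an internal contradiction with a practical consequence. Section 6.5 states a non-reporting rule that conflicts with its own yearly IRB report and with the DSMB's adverse event review and annual summary. A non-fatal serious event judged unrelated has no explicit expedited route on either reading, and no route at all on one of them. With no split by arm required, the DSMB may not see an excess of events that were each attributed to ordinary illness.

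The documents give no rate from which to size the effect; the power figures rest on assumed rates and on 80 and 40 children observed in full. The conclusion itself rests on the wording alone, and on the cited monitoring plans not already resolving it. It concerns safety monitoring and leaves the efficacy analysis untouched. It should be corrected, but it does not show that the board is blind to safety differences.

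**What to change.** In section 6.5, Adverse Events:

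1. State that the exclusion means no individual or expedited report, and reconcile it with the yearly IRB report of non-serious expected events and with the annual DSMB summary.
2. Reword the class of excluded events so that it has one meaning, and state how a non-fatal serious event judged unrelated reaches the DSMB.
3. Require the annual DSMB report to tabulate all logged adverse events and all serious adverse events by randomised arm, whatever the attribution. Give the number of children with at least one event, and events per child-month.
4. State that unrelated events are entered in the adverse event log, which the text does not now say. Carry the same wording into the Data and Safety Management Plan.

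The cost is a few sentences, one table in a report already required, and some extra logging of minor illness at contacts already scheduled in both arms. The table should be read as descriptive: with about 80 v 40 children only large excesses would be statistically detectable, and the difference in contact between arms should be kept in mind.
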